5.1. Sample Size

The performance goal of 34% has been established for the primary safety endpoint, based on a one-sided 97.5% exact binomial test. The 30-day MAE rate is anticipated to be approximately 20%. Under this assumption, the required sample size to achieve a level of 82% power is 86 subjects (**Table 1**).

Assuming 5% attrition over 30 days, enrollment of 91 subjects is necessary for the Primary Analytic Dataset.

Table 1. Sample Size - Primary Safety Endpoint

Measure	
Performance goal	34%
Anticipated freedom from MAE	20%
Significance level	.025
Statistical test	One-sided exact binomial test
Desired power level	82%
Required sample size prior to 5% 30-day attrition rate	86
Required sample size after attrition adjustment	91

A performance goal of 30% has been established for the primary effectiveness endpoint. Anticipating an actual Technical Success rate of approximately 50%, and based upon a one-sided 97.5% exact binomial test, the required sample size to achieve a level of 97% power is 85 subjects (**Table 2**). Since the primary effectiveness endpoint is determined at the time of the index procedure, no attrition has been considered for lost to follow-up or other censoring events. However, the effectiveness endpoint is evaluated in the Primary Analytic Effectiveness cohort, and it is assumed that 3% of enrolled subjects will be treated for DVT in the absence of core laboratory-assessed visible thrombus in the TVS. Assuming a 3% attrition rate for subjects without thrombus, enrollment of 88 subjects will be necessary.

Table 2. Sample Size - Primary Effectiveness Endpoint

Measure	
Performance goal	30%
Anticipated technical success rate	50%
Significance level	.025
Statistical test	One-sided exact binomial test
Desired power level	97%
Required sample size prior to 3% attrition for subjects without thrombus	85
Required sample size after attrition adjustment	88

The required sample size is greater for the primary safety endpoint; 91 vs. 88 subjects. Thus, a total of 91 subjects will be enrolled in the Primary Analysis dataset; providing approximately 91 subjects in the Primary Safety cohort and 88 subjects in the Primary Effectiveness cohort for the primary safety and effectiveness analyses, respectively. The overall power of the study is 80%.

5.2. Derivation of Performance Goal

5.2.1. Derivation of the Safety Performance Goal

The primary safety endpoint of 30-day MAE was available from the following seven studies, summarized in **Table 3**.

Table 3. Safety Performance Goal Literature Summary

Study	Year	Subjects	MAE (%)
Lin	2017	89	35 (39.3%)
Vedantham	2017	336	12 (3.6%)
Schweitzer	2000	50	1 (2.0%)
Elsharawy	2002	18	0 (0%)
Enden	2011	90	13 (14.4%)
Mewissen*	1999	473	60 (12.7%)
Mewissen	1999	312	75 (24.0%)
Engelberger	2015	48	2 (4.2%)
Total		1,104†	198
Weighted Average			23.8%‡

* The second row for the Mewissen study is included to tabulate rethrombosis rate, which was specified for the 312 subjects with acute DVT alone.

†The total number of subjects does not include the 312 subjects in the acute cohort of the Mewissen publication, since this is a subset of the 473 subjects in the series.

‡The MAE weighted average was calculated individually using a random effects model for each component of the composite endpoint and then summed to derive the weighted average for the composite MAE endpoint. For this reason, the denominator for the weighted average is not 1,104, nor does the MAE weighted average represent a simple weighted average of the MAE rates of the individual publications.

The weighted average MAE rate was 23.8%. Using a 10% margin and rounding to the nearest percent, the performance goal for the primary safety endpoint, 30-day freedom from MAE, is 34%.

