| experience, which were furnished to me by | information on the device relating to past non-clinical and clinical the Sponsor, to all physicians and other study personnel responsible to scuss this material with them to ensure that they are fully informed e study. |
| | nation (e.g., source documents and informed consent forms) and all ly, in accordance with local and national regulations. |
| | |
| | |
| | |
| Investigator's Signature | Date |
| | |
| | |
| | |
| | |
| | |

SYNOPSIS

| Protocol Number | 18-001 |
|--|---|
| Study Title | ClotTriever Outcomes (CLOUT) Registry |
| Study Device | ClotTriever® Thrombectomy System |
| Regulatory Status | The ClotTriever Thrombectomy System was cleared in the US under 510(k) number K163549, February 16, 2017. The device is indicated for the non-surgical removal of soft thrombi and emboli from peripheral blood vessels. |
| Sponsor | Inari Medical [name] |
| Primary Study Objective | The primary objective of this study is to evaluate real world patient outcomes after treatment of acute, subacute, and chronic proximal lower extremity deep venous thrombosis (DVT) with the ClotTriever Thrombectomy System. |
| Study Population | The Full Analysis dataset comprises up to 500 subjects with proximal lower extremity DVT. |
| | The Primary Analysis datasets are subsets of the Full Analysis dataset, comprising 91 subjects with unilateral acute or subacute DVT of less than or equal to 6 weeks' duration. |
| | Primary Safety Cohort are subjects in the Primary Analysis dataset who were not treated with thrombolytic or percutaneous mechanical thrombectomy within the prior 3 months. |
| | Primary Effectiveness Cohort are subjects in the Primary Analysis dataset with core laboratory-documented intraluminal thrombus at baseline who have at least one target venous segment (TVS) treated with the study device. |
| Number of Sites | The study will be conducted at up to 50 sites. |
| Study Design | The CLOUT Registry is a prospective, multi-center, observational study of subjects with proximal lower extremity DVT treated with the ClotTriever Thrombectomy System. The Registry will collect data on demographics, comorbidities, details from the DVT diagnosis and treatment, and clinical outcomes through 2-year follow-up. |
| Primary Endpoints (Primary Analysis Cohorts) | Primary Safety Endpoint: Composite of Major Adverse Events (MAEs) through 30 days defined as one or more of the following: |

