10.6 SAFETY PERFORMANCE GOAL DERIVATION

The primary safety endpoint of 30-day MAE was assessed from published studies that treated DVT with pharmacologic means or with other thrombectomy devices. The weighted average MAE rate was 23.8%. Using a 10% margin and rounding to the nearest percent, the performance goal for the primary safety endpoint, 30-day freedom from MAE, was 34%. A detailed analysis of the safety performance goal will be described in the statistical analysis plan.

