5.4.1. Sensitivity Analysis

The primary effectiveness performance goal will be re-calculated by removing the Vedantham data point from Table 4. As such, the weighted average Technical Success rate was 41.3%. Using a 10% margin and rounding to the next percent, the performance goal for the primary effectiveness endpoint of Technical Success was 32%. This performance goal will be used in the sensitivity analysis for the primary effectiveness endpoint.

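### The 34% safety goal rests on a sum of component rates, while the trial counts each subject once; the overlap is uncorrected and no safety sensitivity goal is planned

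*SAP*

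**What the plan says.** **Comparator.** SAP 5.2.1 lists seven publications. Its footnote explains that a random effects model was applied separately "for each component of the composite endpoint and then summed to derive the weighted average for the composite MAE endpoint". It adds that the resulting rate does not have 1,104 as its denominator and is not a simple weighted mean of the study rates. Adding 10 points to 23.8% gives 33.8%, rounded to 34%. Protocol 10.6 reports only the result ("The weighted average MAE rate was 23.8" per cent), does not mention the sum, and refers to the SAP for detail.

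**Trial endpoint.** The Protocol synopsis has "Composite of Major Adverse Events (MAEs) through 30 days defined as one or more of the following", followed by death, major bleeding, new symptomatic PE and rethrombosis. SAP 2.1 has the composite triggered by any of the four categories. SAP 5.3 tests the proportion of subjects with an MAE. A subject with two component events counts once.

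**Sensitivity goals.** SAP 5.4.1 recalculates the effectiveness goal without one data point, moving it from 30% to 32%, and states: "This performance goal will be used in the sensitivity analysis for the primary effectiveness endpoint". No counterpart exists for safety. Neither document corrects the safety rate for overlap or says that the component events fall in different patients.

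**The concern.** The two sides of the safety test are built differently. One is a sum of event rates, the other a proportion of subjects with any event. Within one population the sum is never below the any-event proportion, and it is above it as soon as one patient has two component events. Some overlap is possible by definition: all-cause death is a component, so a fatal major bleed, or a fatal PE that meets the PE definition, scores twice in a sum.

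The device passes by falling below the goal, so any inflation from overlap makes passing easier. Part of the 10-point margin may then be double counting rather than a chosen allowance. Protocol 10.4 requires both primary goals to be met, so this affects what a successful study can claim: that the MAE rate is less than 10 points above a literature rate of the same kind.

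**Working it through.** **Inputs.** SAP 5.1 fixes the goal and the test: "The performance goal of 34% has been established for the primary safety endpoint, based on a one-sided 97.5% exact binomial test". Its planning assumption is an MAE rate of about 20%, for which it says that "the required sample size to achieve a level of 82% power is 86 subjects"; allowing for 5% attrition raises this to 91. From SAP 5.2.1: the 23.8% sum, the 10-point margin and rounding to the nearest percent. Component rates are not given, so those below are assumptions. I read the rule as SAP 5.3 sets it: pass if the exact upper 97.5% limit for the MAE rate is below 34%. Passages that describe 34% as freedom from MAE, or refer to a lower limit, are a separate matter.

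**Step 1: the plan's own figures.** For 86 subjects, the largest c with P(X ≤ c | 86, 0.34) ≤ 0.025 is 20.
- Exact error: P(X ≤ 20 | 86, 0.34) = 2.1%.
- Power: P(X ≤ 20 | 86, 0.20) = 81.5%, against the stated 82%.
- Attrition: 86 / 0.95 = 90.5, so 91.
- Goal: 23.8 + 10 = 33.8, so 34%.

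These reproduce. The 23.8% itself cannot be rebuilt without the component counts.

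**Step 2: from a sum to an any-event rate.** For component rates p₁ to p₄ in one population, max(pᵢ) ≤ P(any) ≤ Σpᵢ. Under independence P(any) = 1 − Π(1 − pᵢ). With the sum fixed at 23.8%, an equal split gives the lowest independence value: 1 − (1 − 0.0595)⁴ = 21.8%.

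| Assumed component rates (%) | Sum | P(any), independent | Plus 10, rounded |
|---|---|---|---|
| 5.95 × 4 | 23.8 | 21.8 | 32 |
| 12, 9, 1.8, 1.0 | 23.8 | 22.1 | 32 |
| 16, 5, 1.8, 1.0 | 23.8 | 22.4 | 32 |
| 22, 1, 0.5, 0.3 | 23.8 | 23.4 | 33 |
| 23.8 alone | 23.8 | 23.8 | 34 |

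Mutually exclusive events leave the goal at 34%. Positive dependence would lower it below the independence value; the documents give nothing from which to estimate that.

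**Step 3: effect on the test.** The 34% rule allows at most 20 events in 86 subjects, or 21 in 91.

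| True MAE rate | Passes 34% rule, n = 86 | Passes 34% rule, n = 91 |
|---|---|---|
| 34% | 2.1% | 1.6% |
| 33% | 3.3% | 2.6% |
| 32% | 4.9% | 4.1% |

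The event limit would be 19 (33% goal) or 18 (32% goal) with 86 subjects, and 20 for either goal with 91. Power at a 20% MAE rate with 86 subjects would be 73.8% for a 33% goal and 64.6% for a 32% goal.

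**The case against.** The case for leaving the plan alone has several parts.

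- **Pooling by component has a rationale.** If publications report different components, study-level totals can understate the composite. The sum is openly disclosed. This stands, and is a reason not to replace the primary goal.
- **The 23.8% is not one population's sum.** It adds four random-effects estimates with different denominators, and one rethrombosis entry comes from a 312-subject acute subset of a 473-subject series. Whether each study reported every component is not shown. A reader might infer that 23.8% is an upper bound on the any-event rate, or that every difference between the two sides favours the device. The documents do not support either: denominators and incomplete reporting could push the figure up or down. Only the summation step has a known direction.
- **The test keeps its stated error.** The goal is a number fixed in advance, and exact error at 34% is 2.1% or 1.6%. A reader might infer an invalid test. That does not follow: the higher probabilities refer to like-for-like goals that the SAP did not set.
- **The effect may be small.** The 21.8% needs an equal split, the extreme under independence. With all 91 subjects evaluable, a 32% or 33% goal changes the limit by one event, and 2.6% is close to nominal. The definitions also restrict overlap: PE requires symptoms and CTPA, and rethrombosis requires imaging of an open and then an occluded segment. This stands as a limit on size.
- **SAP 5.4.1 exists for another reason**, a data point taken from a conference presentation. True, but it shows that the plan accepts a recalculated goal as a supplementary check.

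**Conclusion.** The mismatch is documented and uncorrected. With respect to overlap alone, the 34% goal is the same as a like-for-like goal or more lenient. Assuming four independent components that sum to 23.8%, the leniency is 0 to about 2 points (goal 32% to 34%). A pass at a true rate of 33% or 32% then has probability 3.3% or 4.9% with 86 subjects, and 2.6% or 4.1% with 91.

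Two larger readings should be resisted. The crude Table 3 figure, 198 / 1,104 = 17.9%, lies well below 23.8%, and a reader might take the gap as the double counting. It is not a measure of it: the footnote says the components were pooled separately and on other denominators. A reader might also assume that, say, 10% of summed events are second events in the same patient (23.8% × 0.9 = 21.4%, goal 31%). No figure in the documents supports that share.

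The point therefore warrants a disclosed limitation and one sensitivity comparison, not a new primary goal or sample size.

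**What to change.** Keep 34% as the primary safety goal and leave the success criteria unchanged.

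1. In SAP 5.2.1, state that the summed 23.8% does not correct for patients with more than one component event. Do not call it an upper bound. Show the pooled estimate and the denominator for each component.
2. Add a safety counterpart to SAP 5.4.1. Convert the component estimates to an any-event rate as 1 − Π(1 − pᵢ), and give the range from the largest component to the sum. Apply the same 10-point margin and rounding, and report whether the trial also meets the goal based on the independence value.

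**Cost.** SAP wording and one extra comparison, using component estimates that the footnote says were already calculated; no new subjects or data. The downside is that the stated robustness of a pass may become slightly less favourable.

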5.2.2. Derivation of the Effectiveness Performance Goal

The primary effectiveness endpoint of Technical Success was assessed from published studies that treated DVT with pharmacologic means or with other thrombectomy devices (**Table 4**). The weighted average Technical Success rate was 39.3%. Using a 10% margin and rounding to the next percent, the performance goal for the primary effectiveness endpoint of Technical Success was 30%.

Table 4. Effectiveness Performance Goal Literature Summary

Study	Year	Subjects	Subjects with Near Complete Thrombus Removal
Elsharawy	2002	18	11 (61.1 %)

CLOUD Study: Statistical Analysis Plan

Version 2.0
Jan 28, 2021

Enden	2011	90	68 (75.6 %)
Vedantham*	2017	202	69 (34.2 %)
Engelberger	2015	48	29 (60.4 %)
Mewissen	1999	312	96 (30.8 %)
Schweizer	2000	50	10 (20.0 %)
Total		720	283
Weighted Average			39.3%

* The Vedantham data point was derived from a conference presentation, additional sensitivity analysis will be performed to re-calculate the weighted average of the performance goal without this data point.

5.3. Primary Safety Endpoint Analysis

The primary safety endpoint for this study will be assessed in the Primary Analysis Safety cohort and is a composite endpoint of any MAE within 30 days, as determined by the independent Medical Monitor. The MAE rate is defined as the 30-day rate of all-cause mortality, major bleeding, new symptomatic PE documented by CTPA, or rethrombosis of the target venous segment(s). The MAE rate will be compared to a performance goal with the following null and alternative hypotheses:

$$H_0: P_S \geq PG_S \text{ versus } H_A: P_S < PG_S$$

where P_S is the proportion of subjects with MAE through 30 days and PG_S is the safety performance goal derived from the studies reporting the elements contained in the composite MAE endpoint.

The exact binomial one-sided 97.5% confidence interval will be used to test the primary safety endpoint.

5.4. Primary Effectiveness Endpoint Analysis

The primary effectiveness endpoint is Technical Success, defined by complete or near complete thrombus removal. Thrombus removal is determined by the Marder score at the index procedure, measured after use of the study device but prior to the use of adjunctive devices. Effectiveness will be assessed in the Primary Analysis Effectiveness Cohort^a and will be compared to a performance goal with the following null and alternative hypotheses:

$$H_0: P_E \leq PG_E \text{ versus } H_A: P_E > PG_E$$

where P_E is the proportion of subjects with Technical Success, defined as complete or near complete removal of thrombus with the study device, measured by a venographically-determined reduction of $\geq 75\%$ in the Marder score in the TVSs. The effectiveness performance goal, PG_E , is Technical Success defined in the same manner, derived from published literature.

^a This dataset was designed to exclude those subjects treated who underwent venous thrombectomy for lesions that were non-thrombotic in nature. For instance, those with non-thrombotic May-Thurner lesions that have external compression or scar but who do not have demonstrable intraluminal thrombus. These subjects will remain in the Primary Safety Cohort and will be assessed for safety endpoints but will not be assessed for the effectiveness endpoints.

5.4.1. Sensitivity Analysis

The primary effectiveness performance goal will be re-calculated by removing the Vedantham data point from Table 4. As such, the weighted average Technical Success rate was 41.3%. Using a 10% margin and rounding to the next percent, the performance goal for the primary effectiveness endpoint of Technical Success was 32%. This performance goal will be used in the sensitivity analysis for the primary effectiveness endpoint.

5.5. Secondary Endpoints Analysis

The baseline demographics and anatomic characteristics of the treatment group will be presented with descriptive statistics. The following subgroups will be analyzed:

- Acute (≤ 14 days) versus subacute (>14 days ≤ 6 weeks) versus chronic (>6 weeks)
- Iliofemoral versus femoropopliteal
- Men versus women
- Old versus younger (≥ 65 years, < 65 years)
- Obese versus not obese ($BMI \geq 30 \text{ kg/m}^2$, $< 30 \text{ kg/m}^2$)

5.6. Data Poolability Assessment

The planned analysis for this study will pool data across clinical study sites. Efforts were made to ensure that consistent procedures were used across study sites, including use of the same study protocol, Sponsor monitoring the sites for compliance, and use of identical data-gathering instruments. The appropriateness of pooling the data across centers will be evaluated.^{2, 3} Baseline characteristics will be compared across study sites. For categorical baseline variables, such as sex, a generalized Fisher's exact test or equivalent test will be used and for quantitative variables, parametric or non-parametric analysis of variance (general linear models or an equivalent procedure) will be used.

The above statistical analyses do not result in an impediment to pooling, but rather assess the balance of baseline covariates across study sites. If any baseline covariate is found to be statistically significant by this process, generalized linear mixed model (GLMM) will be used to assess site heterogeneity. This is done by using site a random effect and further quantifying the heterogeneity in terms of Higgin & Thompson's I^2 index.

It may be necessary to combine two or more low enrolling study sites into pseudo-sites to allow these analyses. Sites with fewer than six subjects will be ranked by enrollment from low to high. Starting from the lowest enrollment site, sites will be combined into a pseudo site until the combined size reaches the median enrollment among all sites. This process will be repeated until all resulting sites have enrollment equal to or greater than six subjects. This will be done in a manner to preserve the structure of the study and prevent bias.

Baseline characteristics to be considered as possible covariates will include:

- Age
- Sex
- Coronary artery disease
- Chronic obstructive pulmonary disease
- Myocardial infarction
- Hyperlipidemia
- Cerebrovascular accident
- Hypertension
- Diabetes
- History of tobacco use
- Duration of symptoms
- Isolated iliofemoral DVT versus iliofemoral and distal DVT
- History of hypercoagulable state
- Obesity

If there are relatively few missing data points (e.g., <10%) for a given variable, a simple imputation using the mean (for continuous variables) or median (for dichotomous or categorical variables) of the non-missing values will be done. If there are >10% missing, the variable will be excluded from the imputation analysis.

Poolability analysis will also be performed, comparing the primary endpoints across sites after adjusting for covariate differences. Logistic regression model will be utilized to include unbalanced covariates and sites as an independent variable, and the study outcome as dependent variable to assess outcome differences. If the p-value of site effect is less than 0.10, further analyses will be undertaken to investigate the imbalance of the study outcome.

6. References

3. Paul P. Gallo (2000) CENTER-WEIGHTING ISSUES IN MULTICENTER CLINICAL TRIALS, *Journal of Biopharmaceutical Statistics*, 10:2, 145-163, DOI: 10.1081/BIP-100101019
